Ventricular tachycardia (VT) is an important cause of morbidity and mortality in almost all forms of heart disease[1, 2]. Most of the patients with structural heart disease will have implantable cardioverter defibrillators (ICDs), which reduce the risk of sudden cardiac death[3]. Although ICDs are effective in terminating VT and preventing sudden cardiac death, shocks from ICDs reduce quality of life, and multiple shocks are associated with post-traumatic stress disorder[4, 5]. Most importantly, ventricular arrhythmia episodes and ICD shocks are also associated with increased overall-mortality and progression of heart failure, although the extent to which arrhythmia recurrences actually contribute to adverse outcomes or are simply markers for deteriorating cardiac status remains unclear[6]. Anti-arrhythmic drugs (AADs) are usually the first line therapy for VT. Of all AAD classes, the most commonly used for long-term prevention of VT recurrence are the Vaughan Williams class III AADs (sotalol, amiodarone and dofetilide). Unfortunately, AADs are often insufficient in suppressing VT and they carry a significant adverse effect profile. In cases of recurrent VT, catheter ablation (CA) has been shown to be a safe and effective treatment modality [7]. However, patients with structural heart disease who undergo CA still have substrate that predisposes them to VT recurrences. In addition, catheter ablation lesions heal and evolve over days to weeks, resulting in VT recurrences that are particularly associated with poor outcomes[8-10].

Although most patients undergoing VT ablation are on AADs, it is currently unknown the best management strategy of AADs following VT ablation, i.e., it is unclear if these patients should continue AADs or not.

2. Rationale and Specific Aims

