Catheter ablation is a valuable option to control recurrent VT in patients with structural heart disease [3, 7]. However, after VT ablation the VT substrate remains and ablation lesions heal and evolve over days to weeks, such that some patients will suffer recurrent VT that is associated with worse mortality than patients who remain free of VT. Currently, it is not known if continuation of AADs following VT ablation can prevent these recurrent VT episodes. Of the currently available AADs, class III have the strongest antiarrhythmic profile, however, their significant adverse effect profile limits their use. Therefore, there is equipoise in clinical practice that benefits of class III AADs preventing recurrent VT outweighs the risks of their toxicities.

The specific aim of this pilot study is to obtain preliminary data to evaluate whether the strategy of continuation of class III AADs following CA for VT, improves VT-free survival and reduces readmissions. The goal of this study will be to answer the following question:

Among patients with structural heart disease who undergo VT ablation, does continuation of class III AADs 3 months after ablation, increases VT-free survival compared to discontinuation of antiarrhythmic drug therapy?

3. Hypothesis

We hypothesize that VT-free survival after catheter ablation is greater with continuation of class III AADs.

4. Inclusion/Exclusion Criteria

1. Age >18 years.
2. Able to give written, informed consent
3. Structural heart disease.
4. Implanted and normally functioning ICD or undergoing ICD implant at index admission.
5. Undergoing radiofrequency ablation procedure for sustained monomorphic VT.
6. Primarily on class III AADs for VT.
7. No clinically relevant VT inducible at the end of VT ablation
8. No clinically relevant VT inducible on non-invasive programmed stimulation following VT ablation.

Exclusion Criteria:

1. LV assist device in place
2. Decompensated heart failure and/or requiring continuous inotropic therapy and/or awaiting cardiac transplantation
3. Ongoing acute coronary syndrome.
4. Mechanical prosthetic aortic and mitral valves.
5. Pedunculated or mobile left ventricular thrombus.
6. Persistency of clinically relevant VT at the end of catheter ablation.
7. Absolute contraindications for amiodarone.
8. Participation in other trial.
9. Clinical VT induced on NIPS after VT ablation.
10. Another reason for continuation of class III AADs (i.e., atrial fibrillation).

5. Enrollment/Randomization

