A patient will be identified as a candidate for participation in this study while receiving care at Vanderbilt University Medical Center. The clinical team will contact the patient in-person while being evaluated for VT ablation. The clinical team will ask the patient if they are interested to discuss participation in the clinical trial. If yes, information about participation will be provided by approved research staff. The patient may sign the consent document, decline, or defer until the day prior to ablation. At that time, research staff will again be available to

provide further information and/or obtain consent. Patients who decline participation will continue to receive usual care and the decision to not participate will not interfere with their medical care. Each candidate will receive a copy of the signed consent form. The consent form is presented in Appendix 1.

Patients will have VT ablation. Those with no evidence of clinical VT inducibility after ablation will then undergo Non-Invasive Programmed Stimulation (NIPS) prior to discharge. NIPS will be performed as there is evidence that patients with inducible clinical VT on NIPS after VT ablation have greater risk of VT recurrence [11] and might not be appropriate to withhold anti-arrhythmic therapy for those with inducible VT in NIPS.

Patients that meet inclusion criteria and agree to participate will be randomized and allocated to continue class III AADs or discontinuation using block randomization, stratified by type of AADs used until goal enrollment is achieved. The randomization sequence will be created using STATA 14.2 (StataCorp, College Station, TX, USA) statistical software.

Adherence to study-assigned group will be achieved by clinician education and reminders in routine daily meetings performed by the electrophysiology service.

Before enrollment begins, approval from the Institutional Review Board of Vanderbilt University Medical Center will be obtained, and the trial will be registered in ClinicalTrials.gov.

6. Outcome measures

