The primary outcome will be VT-free survival, a composite of all-cause mortality and VT recurrence one year after VT ablation. Secondary outcomes will be all-cause mortality, VT recurrence, incidence of VT storm, and readmission for heart failure for one year after VT ablation. Both self-terminating sustained VTs (>30 seconds or hemodynamic instability) and VT requiring device therapies for termination will be considered as recurrences when considering VT recurrence.

Subgroup analysis.

The primary and secondary outcomes will also be investigated according to type of cardiomyopathy (ischemic vs dilated) and according to type of AADs.

7. Study Procedures

Enrollment:

At the time of enrollment, baseline information pertaining to symptoms and details clinical presentation, imaging, and heart catheterization procedures will be obtained from examination of their medical record and recorded in a Redcap database

VT ablation procedure

Ablation will be performed according to our usual practice. When feasible, prior to ablation class III AADs will be held for 72 hours prior to ablation per usual practice in our institution.

Ablation will be standardized and performed in all participants per usual care and without any differences in protocol. Briefly, in fasting state patients are taken to the electrophysiology laboratory and are continuously monitored during the ablation with external surface EKG leads.

The procedure will be performed with the usual sterile preparation under moderate sedation or general anesthesia. The left ventricular endocardial cavity will be accessed via either retrograde aortic or trans-septal access. A hexapolar catheter will be positioned in the right ventricular apex. A mapping catheter or a multi-polar mapping catheter will be used to collect voltage and activation data from the left ventricle during sinus rhythm or RV apical pacing. Areas of slow conduction with crowding of isochrones will be outlined.

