Any unanticipated adverse events will be reported by the Principal Investigator according to applicable IRB policy. The PI is fully engaged in the performance of the study and this ensures that adverse events would be readily known by the PI and reported in a timely manner.

10. Study Withdrawal/Discontinuation

If an individual decides to withdraw their consent by informing study staff in writing or verbally, we will withdraw the participant. Contact information for the PI and study staff will be made available to the participant upon enrollment in the consent document.

11. Statistical Considerations and analysis plan

No studies have previously addressed this question; therefore we have no clear expectation on possible effect size and plan to perform this trial as a pilot study aimed at including all patients possible in a time frame of 12-24 months to then inform power size calculations for a larger and blinded clinical trial. We plan to enroll 75 patients per arm.

An intention to treat analysis will be performed. Analysis for the primary outcome will be accomplished by using log-rank statistic. Cox proportional-hazards regression will be used to estimate relative risks and 95% confidence intervals and adjust for differences in baseline outcome predictors. Differences in secondary outcomes will be calculated using log-rank statistic and cox proportional-hazards regression for all-cause mortality, VT-free survival, hospital readmissions and with unpaired t test for VT storm.

Interim analysis of the primary endpoint and drug adverse events will be planned every 6 months from study initiation. An independent statistician blinded to the treatment groups will perform the analysis and report findings to the data and safety monitoring committee who will decide the continuation of the study.

12. Privacy/Confidentiality Issues

A variety of measures will be utilized to ensure participant privacy:

Data will be stored in REDCap using the participant's study ID. Their REDCap data record may contain some identifying information. Subjects will be tracked using their study ID. The identifiable data, excluding date of procedures, will reside as a separate form under the data entry sections labeled "Registration/PHI" within our REDCap database which will allow us to exclude access to the identifiable information, excluding date of procedures, if necessary. Minimal paper records will be kept, and they will be kept locked in a cabinet.

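### Allocation is stratified by AAD type, but the planned log-rank test and Cox model do not use that factor; secondarily, the Cox adjustment should be a supportive model with covariates fixed in advance

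*Combined protocol and SAP*

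**What the plan says.** Section 5 (Enrollment/Randomization) allocates patients "using block randomization, stratified by type of AADs used until goal enrollment is achieved". That is the only stratification factor. The background section names three class III drugs, but no section lists the stratum levels.

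Section 11 states: "Analysis for the primary outcome will be accomplished by using log-rank statistic". It continues: "Cox proportional-hazards regression will be used to estimate relative risks and 95% confidence intervals and adjust for differences in baseline outcome predictors". Neither sentence mentions AAD type or strata. No covariates are listed, no time is given for choosing them, and neither the adjusted nor the unadjusted hazard ratio is named as the main estimate.

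AAD type returns only under the subgroup heading of Section 6: "The primary and secondary outcomes will also be investigated according to type of cardiomyopathy (ischemic vs dilated) and according to type of AADs". Splitting the results by drug does not stratify the overall comparison.

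The trial is a pilot meant to "obtain preliminary data to evaluate whether the strategy of continuation of class III AADs following CA for VT" is beneficial and "to then inform power size calculations for a larger and blinded clinical trial".

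**The concern.** Blocking within AAD type forces the arms to be nearly balanced on that factor. If the factor predicts outcome, this balance makes the treatment comparison less variable than a plain log-rank test assumes. The test then rejects a true null less often than its nominal level, its confidence interval is a little too wide, and some power is lost. A stratified analysis matches the design and recovers this.

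The secondary concern is the Cox adjustment. Its wording most naturally means adjusting for predictors that turn out to differ between arms. The form of the model would then depend on the data. A pilot's hazard ratio and interval matter at least as much as its p-value when they are to inform the next trial, so it should be clear beforehand which hazard ratio is the main one.

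**Working it through.** **No figure to reproduce.** The plan gives 75 per arm with no alpha, power, event rate or effect size. The check is therefore a simulation under stated assumptions.

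**Inputs**
- From the documents: 75 per arm (150 in total), block randomisation within AAD type, one-year follow-up.
- Assumed: AAD strata of 90, 46 and 14; blocks of 4; the two smaller strata at g times the hazard of the largest; hazard ratio (HR) 0.55, the same for every drug; control-arm one-year risk 35%, 45% or 55%; two-sided 5% level.
- Implied events, ignoring stratum differences: 75 × 0.35 + 75 × (1 − 0.65^0.55) = 26.3 + 15.8 = 42 at the low end, and 75 × 0.55 + 75 × (1 − 0.45^0.55) = 41.3 + 26.7 = 68 at the high end.

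**Tests compared.** The unstratified test is U²/V, with U the observed minus expected events in one arm and V its variance, over all patients. The stratified test is (ΣUₛ)²/ΣVₛ, with U and V computed within each AAD stratum and then summed.

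**Results** (20,000 trials per setting; the three entries are for 35%, 45% and 55% risk)

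| g | Power %, unstratified | Power %, stratified | Size % at HR 1, unstratified |
|---|---|---|---|
| 1 | 48.2 / 59.0 / 69.0 | 48.0 / 58.9 / 68.9 | 4.9 / 5.1 / 5.0 |
| 1.5 | 47.4 / 58.7 / 68.0 | 47.7 / 59.1 / 68.6 | 4.8 / 4.9 / 4.8 |
| 2 | 45.8 / 57.8 / 66.1 | 47.1 / 59.6 / 68.3 | 4.7 / 4.6 / 4.3 |
| 3 | 45.1 / 54.2 / 62.8 | 48.5 / 59.4 / 69.2 | 4.0 / 3.7 / 3.5 |

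The stratified test had size 4.8–5.3% throughout, with the stratum of 14 left unpooled. The unstratified 95% interval covered 95.3%, 95.3%, 95.7% and 96.4% at g = 1, 1.5, 2 and 3; the stratified interval covered 95.2–95.3%.

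**Sensitivity.** A separate simulation with two strata (30% of patients in the smaller), 40% control risk and HR 0.6 shows the same pattern. Power is 41.8% unstratified against 43.4% stratified at a 2-fold stratum difference, and 38.8% against 43.3% at 3-fold. Unstratified size is 4.7% and 3.7%.

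**Cox adjustment.** The documents give no selection rule. For illustration, take four independent predictors and adjust for any that differ between arms at p < 0.10. The chance that at least one is flagged is 1 − 0.9⁴ = 34.4%. In 10,000 simulated trials per setting at g = 1.5, with predictors from weak to strong, adjustment moved the hazard ratio in those flagged trials by a median factor of 1.07 to 1.12. The unadjusted 95% interval extends by a factor of 1.62 to 1.88 each way, so the shift is well inside sampling error. The rule had size 4.0–4.8% and changed Cox-test power by −0.2 to +1.1 points.

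With the same four predictors fixed in advance in a stratified Cox model, size at 45% risk was 5.0–5.8%, against 4.7–5.1% unadjusted.

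**The case against.** The best defence of the plan is that the unstratified test is valid and errs on the safe side. The gain from stratifying is under one power point unless AAD type roughly doubles the hazard, and nothing in the documents says that it does. The stratum sizes are assumed, a common treatment effect across drugs was assumed, and a pilot without a power target offers no yardstick for a small gain. The predictors mentioned in Section 11 could include AAD type, and the adjustment could mean one ordinary adjusted model. All of this stands, and it limits the point to a modest improvement.

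It does not remove the point. Section 11 does not say that AAD type is included, and the sponsor considered the factor important enough to stratify on and to examine in subgroups.

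A reader might infer four stronger things that the documents do not support:
- *That the primary test has an inflated error rate.* The departure is in the conservative direction.
- *That fixing Cox covariates buys about 3 to 14 power points.* Gains of that size appear in simulation, but only for the supportive model, and part of them reflects its larger size. In the same simulations, stratifying the Cox model without covariates gained 0.2 to 0.6 points over the unadjusted model.
- *That the open wording means choosing the most favourable model.* Picking the better of the unadjusted and fully adjusted Cox results raised size to 8.5% in one simulation, but nothing in the plan says that this will be done, and the log-rank p-value would be unaffected.
- *That the blinded independent statistician closes the gap.* That provision covers interim analyses and fixes no covariates. Section 7 (Follow-up) also has the study team receiving arrhythmia alarms and device interrogations during the trial.

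**Conclusion.** The point holds as a modest, nearly free improvement. The analysis omits the one factor used to stratify allocation. Stratifying the log-rank test costs 0.1–0.2 power points if AAD type is not prognostic, gains 0.3–0.6 at a 1.5-fold stratum difference, about 1 to 2 at 2-fold and about 3 to 6 at 3-fold, which is an extreme case. These figures rest on assumed event rates, stratum sizes and effect. The mismatch between design and analysis follows from the text alone.

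The Cox wording is secondary. The simulated imbalance rule did little harm. The reason to change it is that covariates kept regardless of balance are a better-defined method than data-triggered adjustment. The change affects only the supportive hazard ratio.

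**What to change.** In Section 11:

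1. Make the primary test a log-rank test stratified by type of AAD. State the stratum levels, and a rule set in advance for pooling small strata, applied to counts over both arms together.
2. Name the Cox hazard ratio stratified by type of AAD, without covariates, as the main estimate, with its 95% confidence interval.
3. Replace the adjustment clause with one supportive Cox model, stratified by type of AAD, with a short list of prognostic covariates kept regardless of balance. Candidates are type of cardiomyopathy, age and, if recorded, ejection fraction. Section 7 says that "baseline information pertaining to symptoms and details clinical presentation, imaging, and heart catheterization procedures will be obtained from examination of their medical record", but does not name ejection fraction, so its availability must be confirmed.
4. Fix that list in a dated SAP, ideally before the first patient is randomised. A later deadline is less secure because the study team sees arrhythmia data as the trial runs.

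The cost is SAP wording and slightly more analysis. Beyond the small power loss if AAD type is not prognostic, the downsides are possible pooling of small strata and an adjusted Cox test that ran slightly liberal (5.0–5.8%), which is the reason to keep that model supportive.

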After catheter ablation, patient's ICD programming to detect and treat VT will be adjusted as per usual practice in our division based on published guidelines[7]. VT detection will be programmed depending on clinical VT rate.

- **If VT is 200 bpm or faster**, detection will be set at 165-171 bpm but without therapy programmed unless HR is > 200 bpm.
- **If VT is slower than 200 bpm**, detection programmed at 20 bpm slower than the known VT cycle length.
- **If the known VT is 140-150 bpm**, set detection at 130 bpm.
- **If the known VT is slower than 140 bpm**, detection should be programmed 10 bpm slower than the known VT.

In addition, will allow delay in therapy of 6-12 seconds. Anti-tachycardia pacing is recommended in all zones.

Follow-up

Patients will be evaluated per usual care after VT ablation by their treating electrophysiologist. This is at two to four weeks after ablation, and then at three months intervals (either in clinic or via remote ICD interrogation) for one year. ICD interrogations will be performed in each visit and we will ask to receive alarms for episodes of VT/VF and therapies delivered. Changes in medical therapy and ICD settings will be at the discretion of the treating electrophysiologist. Our consent form will include request of consent to access remote as well as in-office ICD interrogations. Most of these patients will likely have been already enrolled in a VT registry maintained by the arrhythmia service and this will route us the interrogations with no need to have the patient come for specific appointments with us for this trial.

8. Risks of Investigational Agents/Devices (side effects)

The added risks of continuation of class III AADs include risk of hyperthyroidism, hypothyroidism, hepatotoxicity, pulmonary fibrosis, corneal deposits, optic neuropathy, skin deposition, tremors and increased defibrillator thresholds, polymorphic ventricular tachycardia, torsades des pointes, bradycardia, fatigue, weakness, headache, edema, depression, thrombocytopenia, angioedema, skin rash.

However, most of these patients have been already tolerating these medications over several months/years. Furthermore, we expect that in the long-term, preventing VT will result in reduction of out-of-hospital VT/VF leading to ICD shocks which are associated with reduced quality of life and increased mortality.

9. Reporting of Adverse Events or Unanticipated Problems involving Risk to Participants or Others

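### The unpaired t test planned for VT storm takes no account of time at risk, withdrawal or death, unlike the log-rank and Cox methods planned for the other secondary outcomes in the same sentence

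*Combined protocol and SAP*

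**What the plan says.** Section 6 (Outcome measures) lists among the secondary outcomes "incidence of VT storm, and readmission for heart failure for one year after VT ablation".

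Section 11 (Statistical Considerations and analysis plan) sets the methods for secondary outcomes in one sentence. It assigns "log-rank statistic and cox proportional-hazards regression for all-cause mortality, VT-free survival, hospital readmissions", "and with unpaired t test for VT storm". No other section gives VT storm a different method or explains the exception.

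Three further points bear on this:

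- **Size.** Section 11 states "We plan to enroll 75 patients per arm" and, on the expected difference, "we have no clear expectation on possible effect size".
- **Follow-up.** Section 7 plans a visit two to four weeks after ablation and then contacts at "three months intervals (either in clinic or via remote ICD interrogation) for one year". It adds that "ICD interrogations will be performed in each visit" and that alarms for VT/VF episodes and delivered therapies will be requested.
- **Incomplete follow-up.** Death is part of the primary composite (Section 6), and participants may withdraw at any time (Section 10). There is no rule for how a patient with less than a year of follow-up enters the storm analysis.

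VT storm is not defined, and nothing says whether it is a yes/no event per patient or a count.

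**The concern.** A t test compares two means and has no input for time at risk. The plan foresees both death and withdrawal, so follow-up will vary. For mortality, VT-free survival and readmissions that is handled by time-to-event methods. For storm it is not handled at all.

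Three things are at stake:

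- The storm result would not be on the same footing as the hazard ratios for the other outcomes.
- It would depend on an unwritten choice about patients with short follow-up.
- It would be a poor input to the larger trial that this pilot is meant to inform, because it yields neither a hazard ratio nor a one-year incidence corrected for censoring.

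**Working it through.** The documents give no storm rate, death rate, dropout rate, alpha or power, so there is no planned figure to reproduce. From the documents come 75 per arm and one year of follow-up. All rates below are assumptions, as is a two-sided alpha of 0.05; Section 11 mentions only "estimate relative risks and 95% confidence intervals".

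**1. Yes/no scoring, complete follow-up.** Every possible table at 75 per arm was enumerated. The pooled t test on 0/1 data gave the same decision as Pearson chi-square in all tables with up to 30 events per arm. Its type I error was 4.3% at a storm rate of 3%, 4.9% at 5%, and 5.1% at 10%, 15% and 20%. The mean difference is the difference in proportions.

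**2. Yes/no scoring, incomplete follow-up.** Suppose a patient with no recorded storm enters as 0. Let s be the one-year storm risk without loss and d the one-year risk of death or loss, both with constant hazards: a = -ln(1 - s), b = -ln(1 - d). The expected crude proportion is

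a/(a + b) × [1 - (1 - s)(1 - d)].

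With s = 20%, a = 0.2231:

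- d = 10%: b = 0.1054; 0.2231/0.3285 × (1 - 0.80 × 0.90) = 0.6793 × 0.28 = 19.0%.
- d = 30%: b = 0.3567; 0.2231/0.5798 × (1 - 0.80 × 0.70) = 0.3848 × 0.44 = 16.9%.

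If d is withdrawal, one-year incidence is underestimated by 1.0 and 3.1 points. If the two arms have these two values of d, they differ by 2.1 points although their storm hazards are equal. Over the unequal-follow-up cases tried (s from 10% to 20%) that gap was 0.5 to 2.1 points.

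**3. If d is death alone.** Then the crude proportion is the cumulative incidence of storm with death competing, and the 0/1 mean difference estimates exactly that. A case with some loss as well shows how little separates the two. Assume mean storm hazard 0.30/year in both arms with gamma frailty of variance 1, death hazards 0.05 and 0.30/year, and loss 0.05/year. The marginal storm density is 0.30/(1 + 0.30t)². Integrated from 0 to 1:

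- weighted by exp[-(death + loss)t], the crude proportions are 22.1% and 19.8%, a gap of 2.3 points;
- weighted by exp[-death × t], the cumulative incidences are 22.6% and 20.2%, a gap of 2.4 points.

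**4. Rejection rates at 75 per arm.** Simulation with 4,000 repetitions. In the count version, patients have further storms at an assumed 3/year after the first. Log-rank censors at death or loss.

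| Storm by arm | Death/loss by arm | t test, 0/1 | t test, counts | Log-rank |
|---|---|---|---|---|
| 15%, 15% | 10%, 10% | 4.6% | 4.7% | 4.6% |
| 15%, 15% | 10%, 30% | 6.1% | 5.8% | 5.1% |
| 20%, 20% | 5%, 30% | 7.4% | 6.8% | 5.1% |
| 10%, 25% | 10%, 10% | 66% | 54% | 67% |
| 10%, 25% | 5%, 30% | 51% | 37% | 66% |

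**5. Why power falls in the last row.** The step 2 formula gives:

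- s = 10%, d = 5%: 0.1054/0.1566 × 0.145 = 9.8%.
- s = 25%, d = 30%: 0.2877/0.6444 × 0.475 = 21.2%.

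The 15-point difference shrinks to 11.4 points because the arm with more storms is observed for less time. The direction matters. With the losses swapped, the proportions are 0.1054/0.4620 × 0.37 = 8.4% and 0.2877/0.3390 × 0.2875 = 24.4%. The difference widens to 16.0 points, so no power is lost. The distortion follows whichever arm has the shorter follow-up.

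**The case against.** The strongest reply is that the t test does little harm here. On 0/1 data with full follow-up it is in effect a chi-square test. Under milder assumed imbalances, with the step 3 model, the gap and type I error at 75 per arm are also small:

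- death hazards 0.05 vs 0.10/year: 0.5 points, 5.1%;
- 0.05 vs 0.15/year: 1.0 point, 5.3%;
- 0.10 vs 0.20/year: 0.9 points, 5.2%.

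The 0.05 vs 0.30/year case is one-year mortality of 4.9% vs 25.9%, which no figure in the protocol supports. Even there, type I error is about 6.4%. This is also one secondary outcome in an unpowered pilot. All of that stands, and it limits the priority.

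A reader might infer several stronger things that the documents do not support:

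- **That the t test gives the arm with more deaths a false advantage.** Step 3 shows the same gap in the competing-risk cumulative incidence. It is a real difference in incidence, though not in storm hazard.
- **That storm is a yes/no event and that early leavers count as storm-free.** The first is the natural reading of an incidence, but neither is written. The gap in the plan is the missing definition and rule.
- **That storm is the key harm of stopping the drug.** Section 6 lists it as one of four secondary outcomes, unranked.
- **That the error would grow in the successor trial.** Section 11 gives no size for that trial, which would need its own plan.

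The reply does not cover withdrawal or other incomplete follow-up, count scoring, or the unexplained departure from the methods used for the other outcomes.

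**Conclusion.** The concern holds in a limited form. The t test is a poor match for a one-year incidence with variable follow-up and is inconsistent with the rest of the sentence that prescribes it. It is not a gross error in size: type I error was about 5-7% under every assumed rate tried.

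The practical costs are these:

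- underestimation of one-year incidence when patients withdraw (1.0 point at 10% loss and 3.1 points at 30%, for an assumed 20% incidence, if patients without a recorded storm enter as 0);
- possible loss of power when follow-up differs by arm (about 65% to 50%, or to 37% for counts, in one assumed and rather extreme case, with none for 0/1 scoring when follow-up is equal);
- if storms are counted, a comparison of mean counts in mostly-zero data instead of incidence.

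The reading of Sections 6 and 11 is certain; the sizes rest wholly on assumed rates. Low to moderate priority.

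**What to change.** In Section 11, replace the t-test clause with: *time to first VT storm will be compared by log-rank and Cox regression as for the other secondary outcomes, censoring at death without storm (cause-specific), withdrawal and one year; one-year cumulative incidence by arm will also be reported with death without storm as a competing event.*

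In Section 6, state the definition of VT storm that will be used. Time to first storm cannot be analysed without it.

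The report should say that the two results answer different questions. The cause-specific comparison addresses the storm hazard, while the cumulative incidence will still reflect any difference in mortality.

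The cost is the new clause, one definition and a little extra analysis. No new data collection should be needed, since the ICD interrogations and requested alarms in Section 7 should supply the dates.
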